10.3 Analysis of Laboratory Data

10.3.1 Variables and Units

All laboratory parameters to be collected in this study are listed below. Laboratory parameters will be reported using the standard international (SI) units.

Table 14. List of Laboratory Variables

Laboratory Variables
Hematology
White Blood Cell (WBC) Count
Red Blood Cell (RBC) Count
Hemoglobin
Hematocrit
Platelets count
Neutrophils
Basophils
Eosinophils
Lymphocytes
Monocytes
Bands

Table 14. List of Laboratory Variables (Continued)

Laboratory Variables

Chemistry

Total Bilirubin
Alkaline Phosphatase (ALP)
Serum glutamic oxaloacetic transaminase (SGOT/AST)
Serum glutamic pyruvic transaminase (SGPT/ALT)
Total Protein
Albumin
Glucose
Triglycerides
Blood Urea Nitrogen (BUN)
Creatinine
Uric acid
Sodium
Potassium
Calcium
Inorganic Phosphorus
Creatine Phosphokinase (CPK)
Chloride
Bicarbonate
Cholesterol
LDL cholesterol
HDL cholesterol
International Normalized Ratio (INR) reflux only

Urinalysis

Specific Gravity
pH
Protein
Glucose
Ketones
Blood
Microscopic Examination (if needed)
Urobilinogen

Table 14. List of Laboratory Variables (Continued)

Laboratory Variables
Urinalysis (continued)
Bilirubin
Leukocytes
Nitrites
Other
hs-CRP
QuantiFERON-TB Gold
IgG and IgM
ESR

10.3.2 Analysis of Laboratory Data for Period 1

The laboratory data will be summarized by the "as treated" treatment groups (Upadacitinib 7.5 mg QD, Upadacitinib 15 mg QD, Upadacitinib 30 mg QD, and combined placebo groups) and overall.

10.3.2.1 Assessment of Mean Change from Baseline and Mean Percentage Change from Baseline in Clinical Laboratory Variables

Analyses of mean change from baseline in continuous hematology, chemistry, and urinalysis variables which are measured longitudinally will be performed by visits and by "as treated" treatment group. For each change from baseline analysis, the following summary statistics will be presented for each treatment group: sample size, baseline mean, visit mean, and the mean, standard deviation, and median of the changes from baseline. An ANOVA model with treatment as a factor will be used to test statistical significance for the change from baseline mean among different treatment groups.

In addition, similar analyses will be conducted for mean percentage change from baseline in hemoglobin, NK cells, LDL, HDL and triglycerides.

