### **8.1.5            Safety Analyses**

#### **8.1.5.1            General Considerations**

Safety analyses will be carried out using the Safety Analysis Set. Analyses will be conducted for Period 1 alone, as well as for Period 1 and Period 2 combined. Safety analyses are based on treatments actually received. Safety will be assessed by AEs, physical examination, laboratory assessments, ECG, and vital signs. Frequency tables and lists of subjects with treatment-emergent AEs by preferred term as in the Medical Dictionary for Regulatory Activities (MedDRA) dictionary, by system organ class, by severity, and by relationship to the study drug as assessed by the Investigator will be provided. The changes from baseline in vital signs, physical examination results, and clinical laboratory values will be analyzed in a descriptive manner. Shift of laboratory values from baseline to defined time points will be tabulated.

Missing safety data will not be imputed.

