4.3 Sample Size

Sample size was estimated based on the previous global Phase 2 trial (Study M13-537). Assuming an ACR20 response rate of 46% for placebo group, 62% for low dose group (7.5 mg QD), 68% for middle dose group (15 mg QD) and 80% for high dose group (30 mg QD) of Upadacitinib, the sample size to have 90% power and two-sided alpha of 5% to detect a statistically significant dose-response using Cochran-Armitage test will be 42 subjects per group. And the sample size to demonstrate the superiority of Upadacitinib compared to placebo will be 46 subjects to provide the 90% power and 5% of two-sided alpha. Taking 5% of drop-out rate into consideration, sample size will be 48 per group (total sample size: 192 subjects).

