9.2.3 Key Secondary Efficacy Analyses

Key secondary endpoints at Week 12 are:

1. Change from baseline in DAS28 (CRP);
2. Change from baseline in HAQ-DI;
3. ACR50 response rate;
4. ACR70 response rate;
5. Change from baseline in Short Form-36 (SF-36) Physical Component Score (PCS);
6. Proportion of subjects achieving LDA based on DAS28 (CRP);
7. Proportion of subjects achieving Clinical remission (CR) based on DAS28 (CRP);
8. ACR20 response rate of Week 1;
9. Change from baseline in Functional Assessment of Chronic Illness Therapy-Fatigue (FACIT-F);
10. Change from baseline in Work Instability Scale for Rheumatoid Arthritis (RA-WIS);
11. Change from baseline in morning stiffness (severity).

For binary endpoints, frequencies and percentages will be reported for each randomized treatment group. Similar analyses as for the primary endpoint will be conducted.

For the major RA continuous endpoints DAS28 and HAQ-DI change from baseline, statistical inference will be conducted using analysis of covariance (ANCOVA) coupled

with MI for missing data handling. Specifically, the ANCOVA model will include treatment as the fixed factor, and the corresponding baseline value and the stratification factor prior bDMARD use (Yes/No) as the covariates. For other continuous endpoints, statistical inference will be conducted using the MMRM model as described in Section 9.1.2, with the main stratification factor being prior bDMARD use (Yes/No). From both the MI and MMRM analyses, the LS mean and 95% CI will be reported for each randomized treatment group; the LS mean treatment difference and associated 95% CI and p-value will be reported comparing each Upadacitinib dose group with the combined placebo group.

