10.4 Analysis of Vital Signs

10.4.1 Variables and Criteria Defining Abnormality

Vital sign variables include sitting systolic blood pressure, sitting diastolic blood pressure, pulse rate, respiratory rate, body temperature, and weight. The criteria for potentially clinically significant vital sign findings are presented in [Table 15](#).

Table 15. Criteria for Potentially Clinically Significant Vital Sign Findings

Vital Sign	Category	Criteria for Potential Clinically Significant Vital Signs
Systolic blood pressure	Low	Value \leq 90 mmHg and decrease \geq 20 mmHg from Baseline
	High	Value \geq 160 mmHg and increase \geq 20 mmHg from Baseline
Diastolic blood pressure	Low	Value \leq 50 mmHg and decrease \geq 15 mmHg from Baseline
	High	Value \geq 105 mmHg and increase \geq 15 mmHg from Baseline
Pulse	Low	Value \leq 50 bpm and decrease \geq 15 bpm from Baseline
	High	Value \geq 120 bpm and increase \geq 15 bpm from Baseline
Respiratory Rate	Low	< 10 rpm
	High	> 24 rpm
Body temperature	High	> 39.0 degrees C (102.3 degrees F)
Weight	High	> 7% increase from baseline
	Low	> 7% decrease from baseline

10.4.2 Analysis of Vital Sign for Period 1

Analyses of mean change from baseline in continuous vital sign variables which are measured longitudinally will be performed by visits and by the "as treated" treatment groups of Upadacitinib 7.5 mg QD, Upadacitinib 15 mg QD, Upadacitinib 30 mg QD, and combined placebo groups. For each change from baseline analysis, the following summary statistics will be presented for each treatment group: sample size, baseline mean, visit mean, and the mean, standard deviation, and median of the changes from baseline. An ANOVA model with treatment as factor will be used to test statistical significance for the change from baseline mean among different treatment groups.

The number and percentage of subjects meeting the criteria for potentially clinically significant vital sign values will be summarized by "as treated" treatment group and overall.

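### Period 1 laboratory and vital-sign changes are tested by ANOVA without the baseline value; adding it as a covariate would gain modest precision at almost no cost

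*SAP*

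**What the plan says.** SAP 10.3.2.1 (laboratory, Period 1, by visit): "An ANOVA model with treatment as a factor will be used to test statistical significance for the change from baseline mean". SAP 10.4.2 (vital signs, Period 1) matches it: "An ANOVA model with treatment as factor will be used to test statistical significance for the change from baseline mean". Neither section names another term. The accompanying table in each shows "sample size, baseline mean, visit mean, and the mean, standard deviation, and median of the changes from baseline", so baseline appears in the output but not in the model. SAP 10.3.2.1 adds that "similar analyses will be conducted for mean percentage change from baseline in hemoglobin, NK cells, LDL, HDL and triglycerides".

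The same SAP adjusts its continuous efficacy endpoints for baseline. In 9.2.3, for DAS28 and HAQ-DI, "the ANCOVA model will include treatment as the fixed factor, and the corresponding baseline value" together with prior bDMARD use. The mixed models in 9.1.2 and 9.2.4 also carry the baseline measurement.

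The long-term laboratory and vital-sign sections (SAP 10.3.3.1 and 10.4.3) summarize mean changes without a test. Protocol 8.1.5.1 says: "The changes from baseline in vital signs, physical examination results, and clinical laboratory values will be analyzed in a descriptive manner".

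**The concern.** Subtracting baseline is not the same as adjusting for it. A change score fixes the regression slope on baseline at 1. When the true slope is below 1, as it is for equal SDs and any correlation below 1, subtraction over-corrects. The contrast then keeps noise that the baseline value could remove. A group that happens to start high also tends to fall further through regression to the mean, and this is read as a treatment effect in that sample.

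Comparing the safety of each dose with placebo is the second Period 1 objective. Anemia, neutropenia, lymphopenia, lipid changes, raised creatinine and raised CPK are adverse events of special interest (protocol 6.1.1.3). The group size was set on ACR20 alone, so the precision of these comparisons is whatever 48 per arm happens to give.

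**Working it through.** **The plan's own figure.** The documents give no power or sample size for the safety tests. The relevant figure is the number per group in SAP 4.3 and protocol 8.2.

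- Superiority, 46% (placebo) versus 80% (30 mg), 90% power, two-sided 5%: n = [1.960·√(2·0.63·0.37) + 1.282·√(0.46·0.54 + 0.80·0.20)]² / 0.34² = 40.3, so 41. With continuity correction it is 46, as stated.
- Cochran-Armitage with equally spaced scores and continuity correction: 41.6, so 42, as stated.
- Dropout: 46/0.95 = 48.4. The plan uses 48.

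The three placebo groups are combined (3 × 16 = 48), so each dose-placebo comparison has 48 per arm.

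**Variance.** Let σ0 and σ1 be the baseline and follow-up SDs and ρ their correlation. Per subject:

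- change score: σ0² + σ1² − 2ρσ0σ1
- ANCOVA (large sample): σ1²(1 − ρ²)
- difference: (σ0 − ρσ1)², which is never negative.

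The direction therefore does not depend on equal SDs, but the size does. With σ0 = σ1 = σ the two variances are 2(1−ρ)σ² and (1−ρ²)σ², with ratio (1+ρ)/2.

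**Shift from chance imbalance.** With equal SDs, a baseline mean difference d0 moves the expected change-score contrast by −(1−ρ)·d0. One standard error of a baseline difference at 48 per arm is √(2/48) = 0.204 SD.

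**Results for one dose-versus-placebo contrast.** ρ is assumed.

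| ρ | Variance reduction | n per arm at which ANCOVA matches ANOVA with 48 | ANCOVA power where ANOVA has 80% | Shift from 1-SE imbalance (SD) |
|---|---|---|---|---|
| 0.5 | 25% | 36.0 | 90% | 0.102 |
| 0.7 | 15% | 40.8 | 86% | 0.061 |
| 0.8 | 10% | 43.2 | 84% | 0.041 |
| 0.9 | 5% | 45.6 | 82% | 0.020 |

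A four-arm simulation (48 per arm, 4,000 runs) gave variance ratios of 0.752 at ρ = 0.5 (theory 0.75) and 0.908 at ρ = 0.8 (theory 0.90).

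**Type I error of a nominal 5% pairwise test.** Averaged over randomizations it is 5%. Given a baseline difference of k standard errors, the contrast has mean −(1−ρ)·k·0.204 and variance (1−ρ²)·2/48 in SD units, while the critical value stays at 1.96·√[2(1−ρ)·2/48].

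- k = 0: between 2.4% (ρ = 0.5) and 4.4% (ρ = 0.9).
- k = 1: between 4.8% and 5.0%.
- k = 2: 13.4%, 10.1%, 8.4% and 6.7% at ρ = 0.5, 0.7, 0.8 and 0.9.

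These formulas apply to absolute change. They give no figure for the percentage-change analyses, where baseline is the denominator.

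**The case against.** The strongest reply is that nothing rests on these p-values. The protocol calls the analyses descriptive. SAP 9.1.1 places formal inference in the Period 1 efficacy analysis. No alpha, decision rule or multiplicity claim is attached to the safety ANOVA. On this view the contrast with the efficacy models reflects a different purpose, and dropping the p-values would fit the protocol as well as a better model would. This stands as a limit on importance. It does not remove the point, because the SAP still specifies a significance test where the protocol specifies description, and the two need reconciling in any case.

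The same variables are also watched in other ways:

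- differences with 95% CIs for adverse events of special interest (SAP 10.2.2.1);
- grade shift tables (10.3.2.2);
- Grade 3 or 4 rates with Fisher tests (10.3.2.3);
- liver thresholds (10.3.2.4);
- committee review of unblinded safety data (4.5).

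A reader might infer that safety signals would be missed. The documents do not support that.

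A reader might also infer that the ANOVA is biased or has an inflated error rate. Over randomizations it is unbiased and holds its level. The 13.4% figure applies only given a two-standard-error imbalance at ρ = 0.5.

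Two technical limits also stand. The precision result is a large-sample one: ANCOVA spends one residual degree of freedom (188 to 187), and near ρ = 1 there is no gain. Reporting three contrasts at the four post-baseline visits of SAP Table 5 also gives 3 × 4 = 12 intervals per variable, which is one reason to label them descriptive.

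**Conclusion.** The point holds as a minor efficiency matter, confined to the Period 1 tests in SAP 10.3.2.1 and 10.4.2. The planned ANOVA is valid, but it leaves out a covariate the trial already has. The gain is 5% to 25% of variance for assumed correlations from 0.9 down to 0.5, and a one-standard-error baseline imbalance shifts a contrast by 0.02 to 0.10 SD. These sizes rest on equal baseline and follow-up SDs and on correlations the documents do not give. Strongly correlated variables will sit at the low end.

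The contrast with the efficacy ANCOVA might suggest that the safety model also needs prior bDMARD use. Nothing in the documents shows that this stratum predicts laboratory values or vital signs, and the benefit computed here comes from baseline alone. The long-term analyses, the sample size and the efficacy conclusions are untouched.

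**What to change.** In SAP 10.3.2.1 and 10.4.2, replace the ANOVA with an ANCOVA: change from baseline = treatment + baseline value of the same variable. Report the LS mean difference of each upadacitinib dose from combined placebo, with its 95% CI, by visit. State that these are descriptive estimates, which also brings the SAP into line with protocol 8.1.5.1.

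For the percentage-change analyses of hemoglobin, NK cells, LDL, HDL and triglycerides, include the baseline value as a covariate in the same way. A prior-bDMARD term is not needed.

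The cost is one covariate and a wording change in two sections. No new data, visits or subjects are required.

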10.3.2.2 Assessment of Shift from Baseline in Clinical Laboratory Variables

The baseline and post-baseline laboratory observations will be categorized as Grade 1, Grade 2, Grade 3, and Grade 4 according to OMERACT criteria (Rheumatology Common Toxicity Criteria v.2.0). For creatine phosphokinase, creatinine, NCI CTC criteria will be used.

For each laboratory variable, shift tables will be generated that cross tabulate the subjects' as deemed appropriate by "as treated" treatment group:

- Category of the baseline value versus category of the final value,
- Category of the baseline value versus maximum category.
- Category of the baseline value versus minimum category.

Note that the minimum/maximum category is used, rather than the category of the minimum/maximum value. The two may be different due to variation in the reference range.

No statistical tests will be performed for this analysis.

10.3.2.3 Assessment of Potentially Clinical Significant Laboratory Variables

The criteria for potentially clinically significant laboratory values will be determined by OMERACT criteria of Grade 3 or 4. For creatine phosphokinase, creatinine, NCI CTC criteria will be used.

The number and percentage of subjects meeting the criteria for potentially clinically significant laboratory values will be summarized by "as treated" treatment group and overall. Comparisons of the percentage of subjects experiencing a value meeting the criteria between treatment groups will be performed using Fisher's exact tests. Only p-values ≤ 0.100 when rounded to three digits will be presented.

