- Absolute neutrophil count (ANC) < 1,500/ $\mu$ L
- Platelet count < 100,000 / $\mu$ L
- Absolute lymphocyte count < 800/ $\mu$ L
- Hemoglobin < 10 g/dL

22. History of any of the following cardiovascular conditions:

- Moderate to severe congestive heart failure (New York Heart Association class III or IV);
- Recent (within past 6 months) cerebrovascular accident, myocardial infarction, coronary stenting;
- Uncontrolled hypertension as defined by a persistent confirmed systolic blood pressure > 160 mmHg or diastolic blood pressure > 100 mmHg;
- Any other condition which, in the opinion of the Investigator, would put the subject at risk by participating in the protocol.

23. Positive result of beta-D-glucan or two consecutive indeterminate results of beta-D-glucan.

24. Subject with any planned (elective) surgery within the first 12 weeks of the study.

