J4. Pleuritic pain (pleurisy)	Transient, intermittent symptoms, no treatment or OTC meds relieve	Persistent symptoms, requires prescription meds for relief	Prolonged symptoms, interferes with function, requires frequent narcotic pain relief	Debilitation, requiring hospitalisation
J5. Pneumonitis (pulmonary infiltrates)	Asymptomatic radiographic changes, transient, no treatment required	Symptomatic, persistent, requiring corticosteroids	Symptomatic, requiring treatment including O 2	Debilitating, not reversible; or requiring assisted ventilation
J6. Pulmonary function decreased (FVC or carbon monoxide diffusion capacity – DLCO)	76% – 90% of pre-treatment value	51% – 75% of pre-treatment value	26% – 50% of pre-treatment value	≤ 25% of pre-treatment value

Laboratory Data				
K. Haematology				
K1. Hgb (g/dl) decrease from pre-treatment	1.0 – 1.4	1.5 – 2.0	2.1 – 2.9, or Hgb < 8.0, > 7.0	≥ 3.0, or Hgb < 7.0
K2. Leukopenia (total WBC) × 1000	3.0 – 3.9	2.0 – 2.9	1.0 – 1.9	< 1.0
K3. Neutropenia (× 1000)	1.5 – 1.9	1.0 – 1.4	0.5 – 0.9	< 0.5
K4. Lymphopenia (× 1000)	1.5 – 1.9	1.0 – 1.4	0.5 – 0.9	< 0.5
K5. Platelets (× 1000)	75 – LLN	50 – 74.9	20 – 49.9; platelet transfusion required	< 20; recurrent platelet transfusions
L. Chemistry				
L1. Hypocalcaemia (mg/dl)	1.1 × ULN – 11.5	11.6 – 12.5	12.6 – 13.5; or symptoms present	> 13.5; or associated coma
L2. Hyperglycemia (mg/dl) Fasting	140 – 160	161 – 250	251 – 500	> 500; or associated with ketoacidosis
L3. Hyperkalaemia (mg/dl)	5.5 – 5.9	6.0 – 6.4	6.5 – 7.0 or any ECG change	> 7.0 or any arrhythmia
L5. Hypocalcaemia (mg/dl)	0.9 × LLN – 7.8	7.7 – 7.0	6.9 – 6.5; or associated with symptoms	< 6.5 or occurrence of tetany
L6. Hypoglycemia (mg/dl)	55 – 64 (no symptoms)	40 – 54 (or symptoms present)	30 – 39 (symptoms impair function)	< 30 or coma
L7. Hyponatraemia (mg/dl)	--	125 – 129	120 – 124	< 120
L8. Hypokalaemia (mg/dl)	--	3.0 – 3.4	2.5 – 2.9	< 2.5

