10.3.3.2 Assessment of Potentially Clinical Significant Laboratory Values

Long term laboratory data will be summarized based on the number and percentage of subjects meeting the criteria for potentially clinical significant laboratory values and by the actual treatment received at the time of the event occurrence. The treatment groups are the same as the ones for long term AE analysis as described in Section 10.2.2. A subject can be counted under different treatment groups if he/she switched treatment and experienced potentially clinical significant laboratory values under different treatment groups.

A listing of all subjects with any laboratory determination meeting OMERACT criteria of Grade 3 or 4 will be provided by Grade. For creatine phosphokinase, creatinine, NCI CTC criteria will be used. For each of these subjects, the whole course of the respective parameter will be listed.

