111. Vertigo (dizziness)	Subjective symptoms, transient, intermittent, no treatment	Objective findings, recurrent, meds relieve, occasionally interfering with function	Persistent, prolonged, interfering with daily function; partial response to medication
J. Pulmonary			
J1. Asthma	Occasional wheeze, no interference with activities	Wheezing, requires oral meds, occasional interference with function	Debilitating, requires nasal O ₂
J2. Cough	Transient, intermittent, occasional OTC meds relieve	Persistent, requires narcotic or other prescription meds for relief	Recurrent, persistent coughing spasms without consistent relief by meds, interferes with function
J3. Dyspnea	Subjective, transient, no interference with function	Symptomatic, intermittent or recurring, interferes with exertional activities	Symptomatic during daily routine activities, interferes with function, treatment with intermittent nasal O ₂ relieves
J4. Pleuritic pain (pleurisy)	Transient, intermittent symptoms, no treatment or OTC meds relieve	Persistent symptoms, requires prescription meds for relief	Prolonged symptoms, interferes with function, requires frequent narcotic pain relief
J5. Pneumonitis (pulmonary infiltrates)	Asymptomatic radiographic changes, transient, no treatment required	Symptomatic, persistent, requiring corticosteroids	Symptomatic, requiring treatment including O ₂
J6. Pulmonary function decreased (FVC or carbon monoxide diffusion capacity – DLCO)	76% – 90% of pre-treatment value	51% – 75% of pre-treatment value	26% – 50% of pre-treatment value $\leq 25\%$ of pre-treatment value

Laboratory Data			
K. Haematology			
K1. Hgb (g/dl) decrease from pre treatment	1.0 – 1.4	1.5 – 2.0	2.1 – 2.9, or Hgb < 8.0, > 7.0
K2. Leukopenia (total WBC) × 1000	3.0 – 3.9	2.0 – 2.9	1.0 – 1.9
K3. Neutropenia (× 1000)	1.5 – 1.9	1.0 – 1.4	0.5 – 0.9
K4. Lymphopenia (× 1000)	1.5 – 1.9	1.0 – 1.4	0.5 – 0.9
K5. Platelets (× 1000)	75 – LLN	50 – 74.9	20 – 49.9; platelet transfusion required
L. Chemistry			
L1. Hypercalcaemia (mg/dl)	1.1 × ULN – 11.5	11.6 – 12.5	12.6 – 13.5; or symptoms present
L2. Hyperglycemia (mg/dl) Fasting	140 – 160	161 – 250	251 – 500
L3. Hyperkalaemia (mmol/l)***	5.5 – 5.9	6.0 – 6.4	6.5 – 7.0 or any ECG change
L5. Hypocalcaemia (mg/dl)	0.9 × LLN – 7.8	7.7 – 7.0	6.9 – 6.5; or associated with symptoms
L6. Hypoglycemia (mg/dl)	55 – 64 (no symptoms)	40 – 54 (or symptoms present)	30 – 39 (symptoms impair function)
L7. Hyponatraemia (mmol/l)***	-	125 – 129	120 – 124

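### The Grade 3–4 laboratory count does not require worsening from baseline, so subjects who enter with lymphocytes of 800–900/µL count as events without any change

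*SAP*

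**What the plan says.** SAP 10.3.2.3 defines the event by grade alone: "The criteria for potentially clinically significant laboratory values will be determined by OMERACT criteria of Grade 3 or 4" (creatine phosphokinase and creatinine use NCI CTC grades instead). On the counting it says "The number and percentage of subjects meeting the criteria for potentially clinically significant laboratory values will be summarized" by treatment group. On testing it says: "Comparisons of the percentage of subjects experiencing a value meeting the criteria between treatment groups will be performed using Fisher's exact tests". On display it says: "Only p-values ≤ 0.100 when rounded to three digits will be presented".

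The lymphocyte grades are the same in both documents (row "K4. Lymphopenia (× 1000" of SAP Appendix A and the same row of Protocol Appendix N). In thousands per µL, Grade 1 is 1.5–1.9, Grade 2 is 1.0–1.4, Grade 3 is 0.5–0.9 and Grade 4 is below 0.5. The matching entry limit in Protocol 5.2.2, criterion 21, is "Absolute lymphocyte count < 800" per µL, applied during Screening.

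SAP 10.3.3.2 carries the same criterion into the long-term summary. Values are attributed to the treatment being taken when they occur, and a subject who switches may appear under more than one treatment. It adds: "A listing of all subjects with any laboratory determination meeting OMERACT criteria of Grade 3 or 4 will be provided by Grade".

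**The concern.** A table of potentially clinically significant values is read as what happened on treatment. Here a subject can qualify on a value that was present before the first dose. Read literally, even a baseline value that later improves would qualify, because the section does not say that the value must be post-baseline.

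Other parts of the SAP guard against this. The liver section (10.3.2.4) is limited to post-baseline values. The blood pressure, pulse and weight criteria (Table 15) include a change from baseline. Adverse events must be treatment-emergent (10.2.1).

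Randomisation spreads pre-existing cases about evenly over the arms. They add the same background to each percentage, so the ratio moves towards 1 and the Fisher p-value tends to rise. P-values above 0.100 are left out, so a diluted difference may appear in the table with no p-value at all. In the long-term summary, a placebo subject steady at about 850/µL can be counted under placebo and again under upadacitinib after Week 12, although nothing has changed.

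**Working it through.** **Step 1: which parameters are exposed.** Each entry limit in Protocol 5.2.2, criterion 21, is set against the Grade 3 band in SAP Appendix A.

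| Parameter | Admitted | Grade 3 | Overlap |
|---|---|---|---|
| Lymphocytes | ≥ 800/µL | 500–900/µL | 800–900/µL |
| Neutrophils | ≥ 1,500/µL | 500–900/µL | none |
| White cells | ≥ 2,500/µL | 1,000–1,900/µL | none |
| Platelets | ≥ 100,000/µL | 20,000–49,900/µL | none |
| AST, ALT | ≤ 2 × ULN | from about 3 × ULN | none |
| Haemoglobin | ≥ 10 g/dL | below 8 g/dL, or a fall of 2.1–2.9 g/dL | none |

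Creatinine is limited at entry only through estimated GFR and is graded partly against baseline, so it is not compared here. The grading table leaves 901–999/µL ungraded. If counts are rounded to one decimal in thousands, the lymphocyte overlap reaches about 949/µL.

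**Step 2: group size.** The plan gives no figure for the laboratory comparison, only the group size. SAP 4.3 needs 46 per group for superiority. Comparing 46% with 80% at 90% power and two-sided 5% gives 41 without and 46 with a continuity correction, so that figure reproduces. Allowing 5% drop-out, 46/0.95 = 48.4, and the plan uses 48. The three placebo groups of 16 combine to 48.

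**Step 3: model.** Let b be the share of each arm already Grade 3 at baseline, and e the new-onset Grade 3–4 rate among the rest.

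- As written, the displayed rate is b + (1 − b)e.
- With a worsening rule, the displayed rate is (1 − b)e, taking no baseline Grade 3 subject to reach Grade 4.

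Both rules shrink the risk difference by the factor (1 − b). Only the rule as written changes the risk ratio. With e assumed at 30% versus 5%, the true ratio is 6.0. At b = 5% the table shows 33.5% versus 9.75%, a ratio of 3.4. At b = 10% it shows 37% versus 14.5%, a ratio of 2.6.

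**Step 4: power.** This is the exact power of Fisher's test, 48 versus 48, two-sided 0.05, by full enumeration. New-onset rates of 15% versus 0% are assumed, as is b. At b = 0 power is 75%.

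| b | Shown as written | Power as written | Shown with worsening rule | Power with worsening rule |
|---|---|---|---|---|
| 2% | 16.7% vs 2% | 58% | 14.7% vs 0% | 73% |
| 5% | 19.25% vs 5% | 44% | 14.25% vs 0% | 70% |
| 10% | 23.5% vs 10% | 32% | 13.5% vs 0% | 64% |
| 15% | 27.75% vs 15% | 25% | 12.75% vs 0% | 59% |

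The loss does not depend on a zero placebo rate. With new onset of 30% versus 5% and b = 10%, power is 65% as written and 83% with the worsening rule.

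**Step 5: fixed counts.** Suppose 8 versus 1 new cases among 48 per arm: p = 0.031. Adding two pre-existing cases to each arm gives 10 versus 3 and p = 0.070. Adding five gives 13 versus 6 and p = 0.123, which would not be displayed.

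**The case against.** Most of the case on the other side is fair, and it narrows the point.

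- **Scope.** A reader might infer that all Grade 3–4 laboratory counts are distorted. Step 1 does not support that: among the limits compared, only lymphocytes overlap. Haemoglobin is graded mainly by its fall from pre-treatment.
- **Special-interest events.** A reader might also infer that the lymphopenia analysis of special interest is compromised. It is not. SAP 10.2.2.6 identifies that category by an adverse-event query, and those events must be treatment-emergent.
- **Other tables.** SAP 10.3.2.2 cross-tabulates baseline grade against final, maximum and minimum grade. SAP 10.3.2.1 tests mean change from baseline by ANOVA. SAP 10.3.3.2 lists the whole course of the parameter for each affected subject. A careful reader can therefore separate old cases from new ones. But the shift tables carry no test, and an ANOVA of means does not correct the percentages or p-values in 10.3.2.3.
- **Consistency.** Absolute limits are used elsewhere in the SAP: for respiratory rate and temperature in Table 15, and for the liver thresholds, although the latter are at least post-baseline. The missing condition is therefore not unique to this section.
- **Purpose.** These are unadjusted safety-screening tests, and the trial is sized for ACR20. Power is used here only as a measure of dilution.
- **Information lost.** A worsening rule would drop a fall within Grade 3, such as 0.9 to 0.5. This objection stands, and it is why the absolute count should be kept as well.

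**Conclusion.** The point holds for lymphocytes. The overlap at 800–900/µL follows from the text alone. That unchanged cases pull the risk ratio towards 1 needs only that they are balanced over the arms and that upadacitinib raises the new-onset rate. The repeat count after the Week 12 switch follows from SAP 10.3.3.2.

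The size is not known. The documents do not give the share of subjects who enter at Grade 3 or the new-onset rates, and the model assumes that those who enter at Grade 3 stay counted. On the assumed rates, the rule costs 15 percentage points of power at 2% prevalence (73 − 58), 26 at 5% (70 − 44), 32 at 10% (64 − 32) and 34 at 15% (59 − 25). A reader might instead take the fall from 75% as the loss. That overstates it, because a worsening rule cannot restore the power that would exist if nobody entered at Grade 3.

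This is a cheap improvement to a safety table. It does not touch the efficacy analyses.

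**What to change.** In SAP 10.3.2.3 and 10.3.3.2, base the summarised count, and in 10.3.2.3 the tested count, on post-baseline Grade 3 or 4 values of a higher grade than the subject's baseline. A move from Grade 3 to Grade 4 still counts. Keep the any-Grade-3/4 count and listing alongside, and show by group how many subjects were already Grade 3 or 4 at baseline.

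The cost is about one sentence in each section and a few table rows. Baseline and post-baseline grades are already derived for the shift tables in 10.3.2.2, so no new data are needed. The price is that a fall within Grade 3 leaves the treatment-emergent count; the retained absolute count and listing cover it.
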